12.3.2 Analysis of Secondary Endpoints

The analysis of the following secondary endpoint will be carried out using the safety population:

- The rate (%) of clinical success of all the anchors combined at 12 months post-operative will be summarized as described for the analysis of the primary endpoint. This analysis will also be repeated for each of the anchors used in the study.

12.4 SAFETY ANALYSES

- All safety endpoints will be summarized using the safety population. The incidence of events encountered on-study will be summarized using frequencies and percentages. An overall AE table will summarize the overall AE incidence according to subjects with at least one AE; subjects with at least one AE by worst severity (mild, moderate, or severe); subjects with at least one AE by worst outcome; subjects with at least one AE that led to study discontinuation; subjects with at least one AE by relatedness to investigational device; SAEs; ADEs; ASADEs; USADEs and; SADEs as applicable. A cumulative summary by the number of adverse events encountered overall and within each classification will also be summarized. The incidence of subjects reporting device deficiencies will additionally be summarized.

CONFIDENTIAL AND PROPRIETARY

This document contains information that is confidential and proprietary to Smith & Nephew PLC and Smith & Nephew, Inc. and is intended for use only by Smith & Nephew and its manufacturer. It shall not be reproduced or copied in whole or in part, nor shall the contents be disclosed by any means without prior written permission from Smith & Nephew, nor shall anyone make any use of it that is contrary to the expressed or implied wishes of Smith & Nephew.

Study Protocol—Device	
Safety and Performance of PEEK Anchors (DYNOMITE [®] , SPYROMITE [®] , RAPTORMITE [®] , FOOTPRINT [®] ULTRA PK SL) in Extremities	Number: 2018.15.SMD.PEEK.RET.EXT
	Version: 2.0 05Dec2018
	Page: Page 30 of 54

- Each of the AE classifications will further be summarized by event using frequencies (n) and percentage (%) of subjects with each adverse event as well as the cumulative adverse events/episodes per classification.
- A listing of concomitant medications/therapies will be provided by subject.

Additional summaries of safety endpoints, if applicable, will be described in the SAP.

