5.2 STUDY PURPOSE

This is a retrospective study to evaluate intra-operative, 6 months and 12 months safety and performance of the PEEK anchors (DYNOMITE°, SPYROMITE°, RAPTORMITE°, FOOTPRINT° ULTRA PK SL) for extremities to meet existing MDD/MEDDEV requirements.

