7. OBJECTIVE(S)

7.1 PRIMARY OBJECTIVE

The primary objective of this study is to assess the safety and performance post-market of the PEEK Anchors (DYNOMITE[®], SPYROMITE[®], RAPTORMITE[®], FOOTPRINT[®] ULTRA PK SL) in extremities over a time period of 6 months after intervention.

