7.2 SECONDARY OBJECTIVE

The secondary objective of this study is to assess the safety and performance post-market of the PEEK Anchors (DYNOMITE[®], SPYROMITE[®], RAPTORMITE[®], FOOTPRINT[®] ULTRA PK SL) in extremities over a time period of 12 months after intervention.

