9.3 EXCLUSION CRITERIA

Any one (1) of the following criteria will disqualify a potential subject from participation in the study:

1. Subject is entered in another investigational drug, biologic, or device study or has been treated with an investigational product within 12 months post-operative.
2. Subjects who are < 3 months post-operative.

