10.2.3 Safety Endpoints

Safety endpoints include the collection of the following events from the subjects' medical record:

CONFIDENTIAL AND PROPRIETARY

This document contains information that is confidential and proprietary to Smith & Nephew PLC and Smith & Nephew, Inc. and is intended for use only by Smith & Nephew and its manufacturer. It shall not be reproduced or copied in whole or in part, nor shall the contents be disclosed by any means without prior written permission from Smith & Nephew, nor shall anyone make any use of it that is contrary to the expressed or implied wishes of Smith & Nephew.

Study Protocol—Device	
Safety and Performance of PEEK Anchors (DYNOMITE [°] , SPYROMITE [°] , RAPTORMITE [°] , FOOTPRINT [°] ULTRA PK SL) in Extremities	Number: 2018.15.SMD.PEEK.RET.EXT
	Version: 2.0 05Dec2018
	Page: Page 26 of 54

- All adverse events (AEs) and complications occurring from the time of subject enrollment until study termination or study completion including intra-operative adverse events and complications.
- Device related re-intervention.
- Device deficiency.

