11. STUDY PROCEDURES

11.1 RETROSPECTIVE DATA COLLECTION: 6 MONTHS POST-OPERATIVE (±90 DAYS)

Given the retrospective study design, data will be collected from the medical chart to the extent it is available.

1. Subject should undergo the informed consent process and sign the informed consent *only* if a waiver of consent has not been approved by the IRB.
2. Screen the subject's chart for protocol inclusion/exclusion criteria.
3. Obtain demographic information and a medical history.
4. VAS, ROM.
5. Operative Data Collection – review operative case notes.

CONFIDENTIAL AND PROPRIETARY

This document contains information that is confidential and proprietary to Smith & Nephew PLC and Smith & Nephew, Inc. and is intended for use only by Smith & Nephew and its manufacturer. It shall not be reproduced or copied in whole or in part, nor shall the contents be disclosed by any means without prior written permission from Smith & Nephew, nor shall anyone make any use of it that is contrary to the expressed or implied wishes of Smith & Nephew.

Study Protocol—Device	
Safety and Performance of PEEK Anchors (DYNOMITE°, SPYROMITE°, RAPTORMITE°, FOOTPRINT° ULTRA PK SL) in Extremities	Number: 2018.15.SMD.PEEK.RET.EXT
	Version: 2.0 05Dec2018
	Page: Page 27 of 54

6. Implant Status/ Disposition.
7. Document concomitant medications and/or therapies associated with an AE, SA(D)E.
8. Review the subject’s chart for AEs, SAEs and Device Deficiencies, including inter-operative. AEs, SAEs and DevDs should be documented from the time of surgery through the study duration.

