14. ADVERSE EVENTS AND DEVICE DEFICIENCIES

Adverse Events (AE) related to the study implant, or procedure including Adverse Device Effects (ADE), Serious Adverse Device Effects (SADE), Unanticipated Serious Adverse Device Effect (USADE), and Device Deficiencies (DevD) occurring from the time of the surgery until revision or study completion must be recorded on the appropriate CRF and reported. If the event is known to have been previously reported to Smith & Nephew, this must be noted on the CRF. After enrollment, in addition to all adverse events related to the implant or the procedure, all serious adverse events (SAE), regardless of causality, must be recorded on the appropriate CRF and reported to the Sponsor, and IRB if necessary. Adverse events leading to a revision should be reported at all times regardless of causality.

Adverse Device Effects (ADE) occurring after study completion will be handled as product complaints reportable by the Sponsor and will not be entered into the study database.

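### Section 12.4 plans one pooled on-study event incidence, so AEs, SAEs, ADEs and device deficiencies have no 6-month result, and the nominal 12-month figure has no cut-off or follow-up-based denominator

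*Combined protocol and SAP*

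**What the plan says.** **Objectives.** Section 7.1 sets safety and performance of the anchors "in extremities over a time period of 6 months after intervention" as the primary objective. Section 7.2 sets the same "in extremities over a time period of 12 months after intervention" as the secondary objective. Section 5.2 describes a "retrospective study to evaluate intra-operative, 6 months and 12 months safety and performance of the PEEK anchors".

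**Collection.** Table 1 has a 6-month column (182 ± 90 days) and a 12-month column (365 ± 90 days), and both include AE, SAE, ADE and device-deficiency assessment. Section 11.1 item 8 (6-month review) and section 11.2 item 4 (12-month review) give the same instruction: "AEs, SAEs and DevDs should be documented from the time of surgery through the study duration".

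**Start of collection.** Section 10.2.3 defines the AE endpoint as events "occurring from the time of subject enrollment until study termination or study completion", and adds intra-operative events. Section 14 instead takes implant- or procedure-related events "occurring from the time of the surgery until revision or study completion must be recorded on the appropriate CRF", and asks for all SAEs regardless of causality only after enrollment.

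**Eligibility.** Section 9.3 excludes "Subjects who are < 3 months post-operative", so a subject may enter with about three months of chart.

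**Analysis.** Section 12.4 uses the safety population and states: "The incidence of events encountered on-study will be summarized using frequencies and percentages". It names no time point. It closes by leaving further safety summaries to the SAP where applicable. Section 12.3 gives time-specific results for clinical success only, at 6 and 12 months, for all anchors combined and for each anchor.

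**The concern.** The safety part of the primary objective is tied to 6 months, and the safety analysis is tied to no day. Both chart-review steps collect over one period that starts at surgery and ends with the study. Nothing in collection or analysis therefore assigns an event to the first 6 months.

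The single percentage also mixes subjects followed for very different lengths of time, over a denominator of everyone enrolled. A subject with three months of chart counts the same as one with fifteen. The reported incidence then depends partly on how recent the operations were. A reader who takes it as the 6-month safety result, or as a clean 12-month result, could misjudge the device in either direction.

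**Working it through.** **Plan's own figure.** The documents give no expected safety rate and no calculation for section 12.4. The precision probabilities in section 13 concern clinical success and do not bear on this point. The first check is therefore textual.

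**1. Objective against analysis**

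| Item | 6 months | 12 months |
|---|---|---|
| Objective | 7.1, safety and performance | 7.2, safety and performance |
| Clinical success (no device failure or re-intervention) | 12.3, combined and per anchor | 12.3.2, combined and per anchor |
| AE, SAE, ADE, device deficiency | none specified | 12.4 on-study incidence; nominal only |

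The last row is the gap. The entry under 12 months is nominal because the Synopsis gives the study duration as twelve months of follow-up, while nothing in 12.4 stops counting at day 365 or accounts for subjects who do not reach it.

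**2. Range of charted time (Table 1 and section 9.3)**
- 6-month window: 182 − 90 = day 92 to 182 + 90 = day 272.
- 12-month window: 365 − 90 = day 275 to 365 + 90 = day 455.
- Earliest entry: three months after surgery, close to day 92.

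Charted time can thus run from about day 92 to day 455. It may be shorter for subjects who did not return (section 9.7), since data are taken only as far as the chart holds them (section 11.1).

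**3. Illustration of the extremes.** The rates and the constant hazard are assumptions, not figures from the documents. If a proportion p has an AE by day 182, the proportion by day t is 1 − (1 − p)^(t/182).

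| Assumed p by day 182 | all stop at day 92 | all reach day 455 |
|---|---|---|
| 5% | 2.6% | 12.0% |
| 10% | 1 − 0.90^(92/182) = 5.2% | 1 − 0.90^(455/182) = 23.2% |
| 20% | 10.7% | 42.8% |

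**4. Less extreme cases, p = 10%**
- All subjects followed to day 365: 1 − 0.90^(365/182) = 19.0%.
- Half followed to day 91 (5.1%) and half to day 365 (19.0%): the average is about 12.1%.

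**5. Front-loaded events.** Intra-operative events do not accrue with follow-up. Suppose that 5 of the 10 percentage points are intra-operative and the rest follow a constant hazard. Then 0.95 × r = 0.90, so r = 0.9474 is the event-free proportion over 182 days after surgery. By day 92 the total is 1 − 0.95 × 0.9474^(92/182) = 7.6%. By day 455 it is 1 − 0.95 × 0.9474^(455/182) = 17.0%. The spread narrows from 5.2%–23.2% to 7.6%–17.0%, but the figure still does not estimate the 6-month incidence.

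**The case against.** The other side has several good points.

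- **Time-specific device results exist.** A reader might infer that the study yields no 6-month or 12-month safety figure at all. The documents do not support that. Clinical success at both times captures device failure and re-intervention, and device-related re-intervention is a listed safety endpoint in section 10.2.3. This stands. It does not reach other AEs, SAEs, ADEs or device deficiencies.
- **The on-study figure has a nominal time.** With a twelve-month duration it is in intent the 12-month summary. This also stands. The weakness at 12 months is an undefined cut-off and denominator, not a missing result. The clear omission is at 6 months.
- **The SAP may add the table.** Section 12 requires a SAP before database lock, and 12.4 allows extra safety summaries there. A 6-month cut is therefore unspecified rather than excluded, and it would be wrong to conclude that the study cannot report 6-month safety. Even so, a result that the primary objective needs should not depend on an optional addition.
- **Harm to comparisons.** One might infer that comparisons between anchors or with outside rates would be misleading. Section 12.4 plans neither for safety, so that harm would arise only if someone made such a comparison.
- **Size.** The range from day 92 to day 455 contrasts two cohorts that will not occur in pure form. Section 9.1 enrolls the earliest operations first, so subjects at three months would be the last to enter. The range is an outer bound under a stated assumption.

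**Conclusion.** The concern holds in a limited form. Sections 5.2 and 7.1 name 6-month safety, and section 12.4 specifies no AE, SAE, ADE or device-deficiency incidence to 6 months. For 12 months it gives a nominal figure without a cut-off day or a denominator that reflects follow-up.

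Under a constant hazard and an assumed 10% by day 182, the pooled figure could lie anywhere from 5.2% to 23.2% at the extremes of charted time. It would be about 12% in an evenly mixed cohort of 91-day and 365-day charts. Early clustering of events narrows the spread. These rates are illustrations, and the textual gap does not depend on them.

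A second reading to resist is that section 10.2.3, by starting at enrollment, drops the first months after surgery. That section itself includes intra-operative events, and 11.1, 11.2 and 14 start at surgery, so the documents conflict rather than settle on the later start. The conflict still has to be resolved before any incidence counted from surgery is defined.

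This should be corrected, but it does not undermine the clinical-success endpoint.

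**What to change.** 1. In section 12.4, or in the SAP with a reference from 12.4, tabulate each safety endpoint by onset date: intra-operative; surgery to day 182 (primary objective); surgery to day 365 (secondary objective). Put events after day 365 in a separate row.
2. Give n and % of the safety population. Beside each, show the number of subjects whose charts reach the corresponding window in Table 1. Alternatively, report a time-to-event cumulative incidence at days 182 and 365, with subjects censored at their last chart entry.
3. Make sure the CRF records the onset date of each event. The form is not among the documents, so this cannot be assumed. A date of last chart entry is needed for item 2.
4. Reconcile the start of event collection: enrollment in 10.2.3, surgery in 11.1, 11.2 and 14. At the same time, settle which event types section 14 requires before enrollment and how its stop at revision fits the other sections.

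The collection windows in 11.1 and 11.2 need no rewrite. With onset dates, the cut is made in the analysis. Ending 11.1 at the 6-month review would not give a day-182 cut, because that review can fall anywhere from day 92 to day 272.

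The cost is a few extra table shells, a wording change and, if not already present, an onset-date field (and a last-chart date). Section 23.1.3 places the current version before enrollment and section 12 places the SAP before database lock. The tables can therefore be settled in the SAP, but any new field is best added before charts are abstracted.

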12.5 INTERIM ANALYSES

Not applicable.

13. SAMPLE SIZE JUSTIFICATION

This study is precision-based, thus, the sample size is not based on statistical power calculations. The sample size for this study is determined based on the feasibility of recruitment, enrollment and follow-up considerations. The study is therefore not powered for any statistical hypothesis testing but to have sufficient number of subjects to be able to estimate a clinical success rate of 91% with a 95% confidence interval (CI) of 80% to 100%.

With an assumption of a 91% clinical success rate to be obtained in each of the PEEK anchors and a corresponding 95% CI between 80% and 100%, enrolling between 20 and 120 subjects for each anchor's precision analysis is expected to provide between 15.2% to >95% probability, pending that there is sufficient volume of each type of anchor available. Thus, an overall minimum of 80 and maximum of 480 subjects are to be enrolled into the study, pending that there is sufficient volume of each type of anchor available. Additionally, a minimum of 10 subjects will be enrolled at any investigational site.

CONFIDENTIAL AND PROPRIETARY

This document contains information that is confidential and proprietary to Smith & Nephew PLC and Smith & Nephew, Inc. and is intended for use only by Smith & Nephew and its manufacturer. It shall not be reproduced or copied in whole or in part, nor shall the contents be disclosed by any means without prior written permission from Smith & Nephew, nor shall anyone make any use of it that is contrary to the expressed or implied wishes of Smith & Nephew.

Study Protocol—Device	
Safety and Performance of PEEK Anchors (DYNOMITE [®] , SPYROMITE [®] , RAPTORMITE [®] , FOOTPRINT [®] ULTRA PK SL) in Extremities	Number: 2018.15.SMD.PEEK.RET.EXT
	Version: 2.0 05Dec2018
	Page: Page 31 of 54

14. ADVERSE EVENTS AND DEVICE DEFICIENCIES

Adverse Events (AE) related to the study implant, or procedure including Adverse Device Effects (ADE), Serious Adverse Device Effects (SADE), Unanticipated Serious Adverse Device Effect (USADE), and Device Deficiencies (DevD) occurring from the time of the surgery until revision or study completion must be recorded on the appropriate CRF and reported. If the event is known to have been previously reported to Smith & Nephew, this must be noted on the CRF. After enrollment, in addition to all adverse events related to the implant or the procedure, all serious adverse events (SAE), regardless of causality, must be recorded on the appropriate CRF and reported to the Sponsor, and IRB if necessary. Adverse events leading to a revision should be reported at all times regardless of causality.

Adverse Device Effects (ADE) occurring after study completion will be handled as product complaints reportable by the Sponsor and will not be entered into the study database.

14.1 DEFINITIONS

The categories of adverse events are shown in table 5. The definitions for each of these categories are given in the subsequent sections (see reference within the table).

CONFIDENTIAL AND PROPRIETARY

This document contains information that is confidential and proprietary to Smith & Nephew PLC and Smith & Nephew, Inc. and is intended for use only by Smith & Nephew and its manufacturer. It shall not be reproduced or copied in whole or in part, nor shall the contents be disclosed by any means without prior written permission from Smith & Nephew, nor shall anyone make any use of it that is contrary to the expressed or implied wishes of Smith & Nephew.

Study Protocol—Device	
Safety and Performance of PEEK Anchors (DYNOMITE°, SPYROMITE°, RAPTORMITE°, FOOTPRINT° ULTRA PK SL) in Extremities	Number: 2018.15.SMD.PEEK.RET.EXT
	Version: 2.0 05Dec2018
	Page: Page 32 of 54

Table 5: Categories of Adverse Event

	NOT DEVICE-RELATED	DEVICE- OR PROCEDURE-RELATED	
NON-SERIOUS	ADVERSE EVENT (AE) (SEE 14.1.1)	ADVERSE DEVICE EFFECT (ADE) (SEE 14.1.2)	
SERIOUS	SERIOUS ADVERSE EVENT (SAE) (SEE 14.1.3)	SERIOUS ADVERSE DEVICE EFFECT (SADE) (SEE 14.1.3)	
		ANTICIPATED	UNANTICIPATED
		ANTICIPATED SERIOUS ADVERSE DEVICE EFFECT (ASADE) (SEE 14.1.4)	UNANTICIPATED SERIOUS ADVERSE DEVICE EFFECT (USADE) (SEE 14.1.4)

14.1.1 Adverse Event (AE)

An AE is any untoward medical occurrence temporally associated with the use of an Investigational Product (IP)/Ancillary Product, whether or not considered causally related to that IP/Ancillary Product.

AE is used both to refer to AEs which are non-serious non-IP or procedure-related and as an umbrella term referring to adverse events of all classifications.

14.1.2 Adverse Device Effect (ADE)

An ADE is an adverse event that, in the opinion of the Investigator, is related to the IP or the procedure.

CONFIDENTIAL AND PROPRIETARY

This document contains information that is confidential and proprietary to Smith & Nephew PLC and Smith & Nephew, Inc. and is intended for use only by Smith & Nephew and its manufacturer. It shall not be reproduced or copied in whole or in part, nor shall the contents be disclosed by any means without prior written permission from Smith & Nephew, nor shall anyone make any use of it that is contrary to the expressed or implied wishes of Smith & Nephew.

Study Protocol—Device	
Safety and Performance of PEEK Anchors (DYNOMITE°, SPYROMITE°, RAPTORMITE°, FOOTPRINT° ULTRA PK SL) in Extremities	Number: 2018.15.SMD.PEEK.RET.EXT
	Version: 2.0 05Dec2018
	Page: Page 33 of 54

Not Related - An AE is considered to be not related to the use of an IP or the procedure when the effect is DEFINITELY UNRELATED or UNLIKELY to have any relationship to the use of the IP or the procedure;

Related – An AE is considered to be related to the use of an IP or the procedure when there is a POSSIBLE, PROBABLE, or DEFINITE relationship between the AE and the use of the IP or the procedure.

14.1.3 Serious Adverse Events (SAE) and Serious Adverse Device Effects (SADE)

An AE or ADE is considered a SAE or SADE if, in the view of either the Investigator or the Sponsor, it:

- Results in death.
- Is life-threatening (*NOTE:* The term “life-threatening” in the definition of “serious” refers to an event/reaction in which the subject was at risk of death at the time of the event/reaction; it does not refer to an event/reaction which hypothetically might have caused death if it were more severe).
- Requires in subject hospitalization or results in prolongation of existing hospitalization.
- Results in persistent or significant incapacity or substantial disruption of the ability to conduct normal life functions.
- Is a congenital anomaly/birth defect.
- Is a medically important event or reaction.

Medical and scientific judgment should be exercised in deciding whether other situations should be considered serious such as important medical events that might not be immediately life-threatening or result in death or hospitalization but might jeopardize the subject or might require

CONFIDENTIAL AND PROPRIETARY

This document contains information that is confidential and proprietary to Smith & Nephew PLC and Smith & Nephew, Inc. and is intended for use only by Smith & Nephew and its manufacturer. It shall not be reproduced or copied in whole or in part, nor shall the contents be disclosed by any means without prior written permission from Smith & Nephew, nor shall anyone make any use of it that is contrary to the expressed or implied wishes of Smith & Nephew.

Study Protocol—Device	
Safety and Performance of PEEK Anchors (DYNOMITE°, SPYROMITE°, RAPTORMITE°, FOOTPRINT° ULTRA PK SL) in Extremities	Number: 2018.15.SMD.PEEK.RET.EXT
	Version: 2.0 05Dec2018
	Page: Page 34 of 54

intervention to prevent one of the other outcomes listed in the definition above. Examples of such events are intensive treatment in an emergency room or at home for allergic bronchospasm, blood dyscrasias, or convulsions that do not result in hospitalization; or development of drug dependency or drug abuse.

